1) Turn the light on using the switch	_____	_____	If not, why? (use code) _____ Comments _____
2) Open a drawer	_____	_____	If not, why? (use code) _____ Comments _____
3) Taking a piece of clothing out of the drawer	_____	_____	If not, why? (use code) _____ Comments _____
4) Take the phone off the hook	_____	_____	If not, why? (use code) _____ Comments _____
5) Wipe down (clean) the kitchen countertop	_____	_____	If not, why? (use code) _____ Comments _____
6) Exiting the car (includes only the movement necessary to get up from the seat and stand outside the car after the door is open)	_____	_____	If not, why? (use code) _____ Comments _____
7) Open the refrigerator	_____	_____	If not, why? (use code) _____ Comments _____
8) Open a door by turning the doorknob	_____	_____	If not, why? (use code) _____ Comments _____
9) Using the TV remote control	_____	_____	If not, why? (use code) _____ Comments _____
10) Washing hands (includes lathering and rinsing hands; opening/closing a hand tap)	_____	_____	If not, why? (use code) _____ Comments _____
11) Opening and closing a screw or lever tap	_____	_____	If not, why? (use code) _____ Comments _____
12) Dry your hands	_____	_____	If not, why? (use code) _____ Comments _____
13) Put on the socks	_____	_____	If not, why? (use code) _____ Comments _____
14) Take off your socks	_____	_____	If not, why? (use code) _____ Comments _____
15) Putting on the shoes (includes tying the laces and adjusting the Velcro or straps)	_____	_____	If not, why? (use code) _____ Comments _____
16) Taking off your shoes (includes untying laces and loosening Velcro or straps)	_____	_____	If not, why? (use code) _____ Comments _____
17) To stand up from a chair with armrests	_____	_____	If not, why? (use code) _____ Comments _____
18) Move the chair away from the table before sitting down	_____	_____	If not, why? (use code) _____ Comments _____
19) Pulling the chair towards the table after being seated	_____	_____	If not, why? (use code) _____ Comments _____
20) Raise a glass, bottle (glass or plastic) or can (does not need to include drinking)	_____	_____	If not, why? (use code) _____ Comments _____
21) Brushing your teeth (does not include preparing the toothbrush or brushing dentures, unless the dentures are brushed inside the mouth)	_____	_____	If not, why? (use code) _____ Comments _____
22) Applying foundation, lotion, or shaving cream to the face	_____	_____	If not, why? (use code) _____ Comments _____
23) Using a key to unlock a door	_____	_____	If not, why? (use code) _____ Comments _____
24) Writing on paper (if the hand used for writing before the stroke is the most affected, score the item; if the hand that did not write before the stroke is the most affected, skip the item and mark N/A)	_____	_____	If not, why? (use code) _____ Comments _____

RESEARCH PLAN

25) Carrying an object in your hand (hanging an item over your arm is not acceptable) _____ If not, why? (use code) _____
 Comments _____

26) Using a fork or spoon to eat (refers to the action of bringing food to the mouth with a fork or spoon) _____ If not, why? (use code) _____
 Comments _____ If not, why? (use code) _____
 Comments _____

27) Comb your hair _____ If not, why? (use code) _____
 Comments _____

28) Lifting a cup by the handle _____ If not, why? (use code) _____
 Comments _____

29) Buttoning a shirt _____ If not, why? (use code) _____
 Comments _____

30) Eating half of a sandwich, appetizer, or snack (any food that is eaten with your hands). _____ If not, why? (use code) _____
 Comments _____

TOTAL: _____

Codes for recording "no" responses

1. "I used my unaffected arm the entire time" (check "0").
2. "Someone else did it for me." (mark "0").
3. "I never do this activity, with or without help from others, because it's impossible." For example, combing hair on bald people. (mark "N/A" and remove from the list of items).
4. "I sometimes do this activity, but I haven't had the opportunity since the last time I answered these questions." (repeat the last value assigned for this activity).
5. Non-dominant hand hemiparesis. (only applicable to question 24; mark "N/A" and remove from the list of items).

QUANTITATIVE SCALE	QUANTITATIVE SCALE
0 - I didn't use my weaker arm (I didn't use it).	0 - The weaker arm was never used for that activity.
0.5	0.5
1- I occasionally used my weaker arm, but only very rarely (very rarely).	1 - The weaker arm moved during that activity, but it wasn't helpful (too weak).
1.5	1.5
2 - Sometimes I used my weaker arm, but I did the activity mostly with my stronger arm (rarely).	2 - The weaker arm was of some use during this activity, however, it needed help from the stronger arm or moved very slowly or with difficulty (weak).
2.5	2.5
3- I used my weaker arm approximately half as often as I did before the stroke (half as I did before the stroke).	3- The weaker arm was used for the intended purpose, but the movements were slow or performed only with some (good) effort.
3.5	3.5
4- I used my weaker arm almost as much as before the stroke (3/4 pre-stroke).	4- The movements made by the weaker arm were almost normal, but they weren't as fast or precise as normal (almost normal).
4.5	4.5
5- I used my weaker arm with the same frequency as before the stroke (even before the stroke).	5- The ability to use the weaker arm for this activity was as good as before the stroke (normal).

RESEARCH PLAN

3. Katz Scale (Brazilian version)

For each functional area listed below, check the description that applies (the word "help" means supervision, guidance, or personal assistance).

Functional Area	Independent (I) / Dependent (D)
Taking a bath (bed, bathtub or shower)	
 does not receive assistance (gets in and out of the bathtub alone, if this is the usual way of bathing)	(I)
 receives help to wash only a part of the body (such as the back or a leg)	(I)
 receives help washing more than one part of the body, or cannot bathe alone	(D)
Getting dressed (retrieving clothes, including underwear, from closets and drawers, and handling fasteners, including those of orthotics and prosthetics, when used)	
 The patient picks up their clothes and dresses completely without help	(I)
 The patient picks up their clothes and dresses without help, except for tying shoes	(I)
 receives help to get clothes or get dressed, or remains partially or completely unclothed	(D)
Use of the toilet (going to the bathroom or equivalent place to defecate and urinate; personal hygiene and tidying clothes)	
 Goes to the bathroom or equivalent place, cleans himself/herself and adjusts his/her clothes without help (may use objects for support such as a cane, walker or wheelchair and may use a bedpan or urinal at night, emptying it in the morning)	(I)
 receives assistance to go to the bathroom or equivalent location, or to clean themselves, or to adjust their clothes after defecation or urination, or to use a bedpan or urinal at night.	(D)
 does not go to the bathroom or equivalent for physiological eliminations.	(D)
Transfer	
 Gets out of bed and lies down, sits down and stands up from a chair without assistance (may be using an object for support, such as a cane or walker)	(I)
 lies down and gets out of bed and/or sits down and gets up from a chair with help.	(D)
 doesn't get out of bed	(D)
Continence	
 It completely controls urination and defecation	(I)
 There are occasional "accidents".	(D)
 needs help to maintain control of urination and defecation; uses a catheter or is incontinent.	(D)
Food	
 The patient feeds themselves without help	(I)
 The patient feeds themselves, but receives help cutting meat or spreading butter on bread	(I)
 receives assistance with feeding, or is fed partially or completely through the use of catheters or intravenous fluids.	(D)

Interpretation (Katz & Apkom):

RESEARCH PLAN

0: independent in all six functions; **1:** independent in five functions and dependent in one function; **2:** independent in four functions and dependent in two; **3:** independent in three functions and dependent in three; independent in two functions and dependent in four; **5:** independent in one function and dependent in five functions; **6:** dependent in all functions.

4. Structured questionnaire

I - Identification

- 1) Name: _____
- 2) Date of birth: ____ / ____ / ____
- 3) Medical record number: _____
- 4) Age: _____
- 5) Nationality: _____
- 6) Sex: ()Male ()Female
- 7) Race/color: ()Asian ()Indigenous ()White ()Black ()Others
- 8) City of residence: _____
- 9) Neighborhood: _____
- 10) Profession: _____
- 11) Current occupation: _____
- 12) Telephone: _____
- 13) E-mail: _____
- 14) Reference physician: _____
- 15) Caregiver/responsible family member: _____
- 16) Dominance: ()Right ()Left-handed ()Ambidextrous

II - Family

- 17) Marital status: ()Single ()Married/Living with partner ()Divorced/Separated ()Widow(er) ()Others
- 18) Do you have children?: ()Yes ()No
- 19) Number of Children: _____
- 20) Currently, where and how do you live?: ()At home or in an apartment, alone ()At home or in an apartment, with parents and/or relatives ()Living in a house or apartment with a spouse ()In another type of housing
- 21) Can you move around between the rooms of the house? ()Yes ()No
- 22) Do you have a caregiver or family member who assists with daily tasks? ()Yes ()No
- 23) Do you have a family history of stroke? ()Yes ()No

III - Education

- 24) Level of education: ()Illiterate ()Can read and write ()Elementary education ()High School ()Higher education ()Postgraduate studies

IV - Income

- 25) Do you have health insurance? ()Yes ()No
- 26) Income: ()less than minimum wage ()up to one minimum wage ()between 2 and 3 minimum wages ()4 to 5 minimum wages ()more than 6 minimum wages

V - Assistive Technology

- 27) Assistive technology: ()Wheelchair ()Walker ()Single-point cane ()Forearm crutch ()Shower chair ()Hearing aid ()Orthosis ()Other - Specify
- 28) Do you wear corrective lenses?: ()Yes ()No
- 29) Uses dentures: ()Yes ()No

VI - Health condition

- 30) Injury time: _____
- 31) Date of injury: _____

RESEARCH PLAN

32) Type of stroke: ()Ischemic ()Hemorrhagic
 33) Medications: ()Antihypertensive ()Antiplatelet agent ()Anti-inflammatory ()Antidepressant ()Antipsychotic ()Antidiabetic ()Anticonvulsant ()Sedative ()Analgesic ()Diuretic ()Other - Specify
 34) Associated diseases: ()Rheumatological ()Genitourinary ()Endocrine ()Gastrointestinal ()Cardiovascular ()Respiratory ()Other - Specify
 35) Current pain?: ()Yes ()No
 36) Pain location: _____
 37) Presence of sensory alterations: ()Yes ()No
 38) Location of sensory alteration: _____
 39) Currently smokes: ()Yes ()No
 40) Former smoker: ()Yes ()No
 41) Consumes alcoholic beverages: ()Yes ()No

5. Schedule of appointments (intervention group)

Service Number	Intervention Focus	Duration (min)	Description	Responsible
1	Initial assessment (in person)	60	Application of the structured questionnaire, and the scales Instrumental Activities of Daily Living Scale, Katz Scale, and Motor Activity Log.	Independent researcher
2	Guidelines on the importance of mobility/positioning/posture of the body and the affected upper limb (telehabilitation)	45	To provide guidance on the importance of body and affected upper limb mobility/positioning/posture for: prevention and treatment of muscle contractures; improvement of joint mobility; improvement of blood circulation; reduction of spasticity; prevention of secondary injuries; improvement of neuromuscular function and coordination; prevention of muscle atrophy.	Researcher responsible
3	Nutrition; Mobilization; Cognitive/recreational activity (telerehabilitation)	45	Guidelines on techniques for independent feeding (opening packages, preparing and serving food).	Researcher responsible
4	Self-care; Mobilization; Cognitive/recreational activity (telehabilitation)	45	Guidance on independent personal hygiene techniques (combing and tying hair, brushing teeth, shaving, applying makeup), positioning of the affected upper limb, and possible adaptations.	Researcher responsible
5	Leisure; Mobilization; Cognitive/recreational activity (telerehabilitation)	45	Guidance and discussion about possible leisure activities.	Researcher responsible
6	Bathing and toilet use; Mobilization; Cognitive/recreational activity (telerehabilitation)	45	Guidelines on techniques and adaptations for independent bathing and toilet use.	Researcher responsible

RESEARCH PLAN

7	Upper Clothing; Mobilization; Cognitive/Recreational Activity (telerehabilitation)	45	Guidelines on techniques and adaptations for autonomy in dressing upper limbs.	Researcher responsible
8	Lower garment; Mobilization; Cognitive/recreational activity (telerehabilitation)	45	Guidelines on techniques and adaptations for independent dressing of lower limbs.	Researcher responsible
9	Final instructions (for family/caregiver when necessary). Reinforcing safety aspects during activities (telerehabilitation).	45	Guidelines regarding finals, questions, and safety aspects.	Researcher responsible
10	Final assessment (in person)	60	Final application of the Scale of Instrumental Activities of Daily Living, Katz Scale, and Motor Activity Log.	Independent researcher

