To identify telerehabilitation as a strategy for optimizing care and access to public rehabilitation services.

METHODS

In order to answer the research objectives, a randomized controlled trial study was chosen. This is a pilot study that will be developed through the proposal of telerehabilitation sessions for patients on a waiting list, with a medical prescription, for Occupational Therapy care at the IMREA FMUSP, linked to the Lucy Montoro Rehabilitation Network.

A convenience sample will be used (20 users, divided equally into two groups), considering that patients awaiting care will be subject to the research eligibility criteria and will be selected in descending order (selected in reverse chronological order from the waiting list) to allow sufficient time for the intervention. If a study participant, regardless of the group to which they belong, is called to begin in-person Occupational Therapy care, a final assessment will be applied, concluding the follow-up.

Data collection for initial and final assessments will be conducted by an independent researcher, not involved in the study, allowing for a single-blind study. Participants will be divided into two groups using randomization: intervention and control. The first group (intervention) will participate in one 45-minute session per week for eight weeks. During this

RESEARCH PLAN

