time, participants will receive guidance and perform therapeutic activities to improve occupational performance. The second group (control) will remain on the waiting list, without a specific intervention, as they were already waiting for care. Both groups will undergo initial assessments in the first session and final assessments in the last session. Jerry Dallal's randomization tool (Dallal, 2020) will be used to classify participants into the first and second groups. Allocation, at a 1:1 ratio, will be conducted by an independent researcher who will not participate in data collection or statistical analysis. The concealed allocation will be implemented using sequentially numbered, opaque, and sealed envelopes. A blind evaluator will open the sealed envelopes after the Informed Consent Form (ICF) has been signed and will conduct the evaluation of the participant in person. Those participants selected by lottery, belonging to the intervention group, will be given a schedule with the dates and topics that will be addressed in each session. Participants in the control group will sign the ICF and complete the structured questionnaire and rating scales.

The following research protocols will be used as data collection instruments: Katz Scale (Lino et al., 2008) for assessing ADLs; Scale of Instrumental Activities of Daily Living (Dos Santos; Júnior, 2008) for measuring performance in IADLs; and Motor Activity Log (MAL) for assessing hand motor function (Saliba et al., 2011). The study will be conducted according to the Consolidated Standards of Reporting Trials (CONSORT) and the Standard Protocol Items: Recommendations for Interventional Trials (SPIRIT).

Participants will also be given a structured sociodemographic questionnaire, developed by the researcher, to collect demographic data, including age, sex, educational level, and other data. Similarly, clinical data will be collected, such as the duration of hemiplegia, laterality of the affected body, etiology, hand preference, risk factors, and motor stages according to the Brunnstrom model (Naghdi, 2010). The questionnaire will be administered by the independent researcher at the time of randomization.

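### Motor Activity Log code 4 repeats a previous item score, but with two interviews there is none at baseline and only the baseline score at the final visit

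*Combined protocol and SAP*

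**What the plan says.** The Methods section lists the MAL as one of three outcome scales, with the Katz scale and the instrumental activities scale: "Motor Activity Log (MAL) for assessing hand motor function". None of the three is named primary.

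Appendix 2 prints the 30-item score sheet and five codes for a negative answer. Code 4 applies when the person says "I sometimes do this activity, but I haven't had the opportunity since the last time I answered these questions", and the instruction is to "repeat the last value assigned for this activity". The other codes work differently. Codes 1 (other arm used) and 2 (someone else did it) score 0. Codes 3 (activity impossible) and 5 (item 24 only) mark the item N/A and remove it.

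On timing, the Methods section says "Both groups will undergo initial assessments in the first session and final assessments in the last session". In Appendix 5, service 1 is "Application of the structured questionnaire, and the scales Instrumental Activities of Daily Living Scale, Katz Scale, and Motor Activity Log" and service 10 is "Final application of the Scale of Instrumental Activities of Daily Living, Katz Scale, and Motor Activity Log". Services 2 to 9 list no scale. The intervention is "one 45-minute session per week for eight weeks". The interval can be shorter in either group, because if a participant "is called to begin in-person Occupational Therapy care, a final assessment will be applied, concluding the follow-up".

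DATA ANALYSIS compares group means by t-test or Wilcoxon test. It gives no MAL scoring rule, no rule for unrated items and no sensitivity analysis. The form ends in a single total line.

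**The concern.** Code 4 takes both its reference period and its score from an earlier interview. That suits repeated interviewing, but this trial has one interview before treatment and one after.

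At baseline the instruction cannot be followed. Different assessors, or one assessor on different days, could enter 0, N/A or a guess, and each choice has a different effect on the score. At the final visit the instruction can be followed, but it places a pre-treatment rating in the post-treatment score. This happens whether the analysis uses change or final values, because the carried item is a pre-treatment score in both. An item coded 4 at both visits never acquires a value.

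At stake is the accuracy of one of the three outcome scales, the only one directed at hand function, in a trial of 20 people.

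**Working it through.** The plan states no figure on this point. It gives no alpha, power, effect size or SD either, so there is nothing to reproduce. The check applies code 4 at each scheduled MAL interview.

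**Inputs from the documents:** 30 items (Appendix 2); two MAL interviews (Methods; Appendix 5, services 1 and 10); about eight weeks between them (Methods), or less after an early final assessment.

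**Assumed, because the documents are silent:** the number k of items coded 4, taken as 1 to 3; a true item level of 2.0; similar true change on every item.

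**Applying the rule**

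| Visit | Earlier MAL interview | Result of code 4 |
|---|---|---|
| Initial (service 1) | none in the trial | no score to repeat |
| Final (service 10) | initial only | final item = baseline item, so change = 0 |

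**Baseline, improvised 0.** Mean item score = 2.0 × (30 − k)/30.
- k = 1: 2.0 × 29/30 = 1.93, which is 0.07 too low.
- k = 3: 2.0 × 27/30 = 1.80, which is 0.20 too low.

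If the item is rated normally at the final visit, the shortfall reappears as a false gain of 0.07 or 0.20.

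**Baseline, item dropped.** The mean over the rated items stays at 2.0. A sum falls by 2 points per item: 60 − 2 = 58 for k = 1 and 60 − 6 = 54 for k = 3. The choice between mean and sum therefore matters, and the plan does not make it.

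**Final visit, score carried forward.** Share of true change retained = 1 − k/30.
- k = 1: 29/30 = 97%.
- k = 2: 28/30 = 93%.
- k = 3: 27/30 = 90%.

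**Denominator.** Codes 3 and 5 can reduce the number of items below 30, with little effect on these figures. With 29 items and k = 3, the share retained is 26/29 = 90%.

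**Direction.** If code 4 is about equally frequent in both arms, changes in both arms are scaled down alike and the group difference shrinks toward zero. If control participants have more code 4 items and would otherwise have improved, freezing those items widens the difference.

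**The case against.** The strongest reply is that code 4 will seldom be used. It covers lack of opportunity only. Use of the other arm or another person's help scores 0, and impossible activities are removed, so most non-use never reaches code 4. Most of the 30 items are household tasks such as switches, drawers, taps, socks and cutlery, and about eight weeks without an opportunity for several of them is unlikely. This stands, and it is why the range above stops at 3 items. An early final assessment shortens the interval, but the plan does not say by how much or for how many.

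A second objection is that the dilution formula is only illustrative. The quantitative scale rates actual use of the weaker arm, so an activity with no opportunity has no observed change to retain. This also stands. The percentages show scale and are not estimates.

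Four stronger readings are tempting, and the documents do not support them:
- **That admission regardless of Rankin score makes code 4 common.** Disability is not lack of opportunity. Such patients would mostly fall under codes 1 and 2.
- **That the endpoint is filled with pre-treatment scores.** Only code 4 items are affected, on one of three scales with none named primary.
- **That the MAL difference is necessarily pulled toward zero.** This requires similar code 4 frequency in both arms.
- **That the baseline interview has no recall window.** Appendix 2 reproduces the score sheet and codes without interviewer instructions, and the cited Brazilian adaptation is not part of the documents. One can say only that the plan prints no window.

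Fidelity to the printed instrument does not answer the remaining point. A faithful copy of the form still contains a rule that this trial cannot carry out at its first interview.

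**Conclusion.** The point holds in a narrow form. With two MAL interviews, the printed rule has nothing to repeat at baseline and can only copy the pre-treatment score at the final visit, and nothing in the analysis section repairs this. That conclusion follows from the text and the schedule and needs no assumption.

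The size does rest on assumptions. It is about 0.07 on the mean item score for each item wrongly entered as 0 at baseline (true level 2.0, 30 items), and a loss of 3% to 10% of the true change for 1 to 3 carried-forward items (similar change across items). The frequency of code 4 is unknown and probably low, and the direction of bias in the group difference is not fixed. Severity is minor: a cheap clarification to a 20-person pilot.

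**What to change.** Add a scoring note to Appendix 2 and a line to DATA ANALYSIS:

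1. At baseline, mark a code 4 item N/A and remove it, as codes 3 and 5 already do.
2. At the final visit, treat a code 4 item as missing and do not copy the baseline score.
3. Score the quantitative and qualitative scales separately, each as the mean (not the sum) of the items rated at both visits.
4. Report the number of code 4 items by visit and arm. Give the printed carry-forward scoring as a sensitivity analysis where a baseline value exists.
5. State one look-back window for both interviews, in line with the adapted instrument's instructions.

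The cost is a disclosed departure from the printed code 4 and slightly fewer items for some participants, who will then be scored on somewhat different item sets. A short look-back window would also raise the number of no-opportunity answers, so its length should be chosen with that in mind. The note is best added before the first interview. Because the form has a field for the code, steps 1 to 4 can still be applied later if the code was recorded, but step 5 cannot be applied to interviews already held.

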The research presents a low risk of harm to participants, as it involves remote guidance, not exposing the user to any type of invasive procedure or risk associated with travel for appointments. However, the nature of stroke can result in significant variations in the cognitive and physical abilities of patients, which may interfere with adherence to and development of therapeutic interventions through telerehabilitation. Regarding the proposal to conduct remote appointments via video call platforms, there is a risk that sessions may be compromised due to technical and connection problems at the time of the sessions, potentially leading to difficulties in understanding and hindering the visualization and interpretation of instructions, inhibiting or hindering participation. Interruption of remote appointments will occur due to health problems and personal issues of the patient that prevent their participation; recurring technical issues that prevent the patient from accessing sessions; lack of interest from the research participant in continuing treatment; as well as the start of in-person Occupational Therapy appointments. To minimize such risks, a set of measures and/or procedures will be taken to ensure the privacy, confidentiality, and security of participants and their information. These are: i) data collection through scales and the structured questionnaire will be carried out manually, and only the researchers involved in the research will have access; ii) data collected manually will be digitized and stored on institutional servers; iii) personal information of participants related to the information provided will not be part of the research records, including any information that could be used to establish, identify, or reveal the participant's identity, or any other data that may be requested by the participant will be discarded from the research records; iv) depending on the degree of difficulty the patient has in performing the activities through telerehabilitation, it will be necessary for them to have a family member or caregiver present during the session; v) the participant will have complete freedom not to participate or to withdraw their consent at any time, even after the conclusion of the research, without any penalty, and will have confidentiality and privacy. vi) Nevertheless, in the event of harm or distress, the researcher is committed to providing support and referring participants to the physician responsible for the patient, without any expenses for the participants.

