
BENEFITS

The benefit of this research to individuals diagnosed with stroke and to occupational therapists working in the rehabilitation field within the Brazilian Unified Health System (SUS) is direct. For patients, it represents a possible structuring of another healthcare pathway in the

RESEARCH PLAN

rehabilitation process. For professionals, the research is linked to expanding knowledge about the use of telehealth for rehabilitation interventions within the SUS. The benefits for other professional categories are indirect, through support for research aimed at developing and improving the skills necessary for providing virtual healthcare services.

DATA ANALYSIS

The data collected through assessments and the structured questionnaire will be organized and classified according to their variables in digital spreadsheets. Subsequently, this data will be stratified using STATA software for statistical analysis. The effects of telehealth and the occupational performance of the participants will be determined by comparing the means between the intervention and control groups, as observed in the study assessments. The analysis method will be defined as either the Student's t-test or the Wilcoxon test, depending on whether the data are parametric or non-parametric, after normality tests using Shapiro-Wilk and evaluation of histograms or q-q plots. The other objectives will be analyzed descriptively. The information obtained will be correlated with the bibliographic material collected, aiming to integrate the results and draw conclusions about the use of telerehabilitation by occupational therapists.

FINANCIAL RESOURCES

The research will not receive direct public or private funding. Expenses related to equipment, personnel, materials and supplies, among other costs necessary for the project, are already integrated into the routine of the health service. Thus, these costs will not represent an additional burden on the institution's operation.

TIMELINE

The planned research schedule will be executed, as per Table 1, if the project is approved by the CEP/CONEP System. The same will occur within a period of 11 months.

Stage Identification	Month										
	0 1	0 2	0 3	0 4	0 5	0 6	0 7	0 8	0 9	1 0	1 1
Field research - participant recruitment and randomization	X	X									
Field research - initial application of questionnaires and scales (group, intervention, and control)	X	X									

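### No adverse event is asked about, recorded or counted in either arm, and with eight planned contacts against none between assessments, harm noted informally would be ascertained unequally

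*Combined protocol and SAP*

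**What the plan says.** RISK ANALYSIS rates the risk as low because guidance is remote, "not exposing the user to any type of invasive procedure or risk associated with travel for appointments". Its provision for harm that has occurred is: "in the event of harm or distress, the researcher is committed to providing support and referring participants to the physician responsible for the patient". The same section lets remote sessions be interrupted for health reasons and calls for a carer at sessions that a patient finds difficult. The eligibility criteria require clinical stability, and service 9 in Appendix 5 goes over safety.

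METHODS has the structured questionnaire given once, when the participant is randomized. Its health section (Appendix 4, part VI) contains "35) Current pain?: ()Yes ()No", followed by pain location, sensory alteration and its location (items 36-38). Service 10 in Appendix 5, the closing visit, consists of "Final application of the Scale of Instrumental Activities of Daily Living, Katz Scale, and Motor Activity Log". The questionnaire is not repeated.

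METHODS gives the intervention arm one session a week for eight weeks and leaves controls on the waiting list. Both arms have an initial and a final assessment, and anyone called to in-person care is assessed at that point and leaves follow-up. On numbers: "A convenience sample will be used (20 users, divided equally into two groups". On analysis, DATA ANALYSIS compares group means ("The analysis method will be defined as either the Student's t-test or the Wilcoxon test") and describes the remaining objectives. It does not mention harm.

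**The concern.** The general objective is to determine the effects of the service, and unwanted effects are among them. The plan itself treats injury as relevant: service 2 names "reduction of spasticity; prevention of secondary injuries" among its aims, sessions 3 to 8 all list mobilization, and patients may enter at any Rankin score provided they are clinically stable. Yet nothing in the data collection would show whether falls, injuries, pain, new strokes or admissions were more or less frequent with telerehabilitation than on the waiting list.

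Two consequences follow. The baseline pain and sensory answers cannot be used to measure change. And if the investigators later describe problems that came up, those will come mostly from the arm that speaks to a therapist every week. Such a list could look like an excess in the intervention arm when it reflects only more opportunity to mention things. Harms not asked about at the final assessment are hard to recover reliably afterwards.

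**Working it through.** **1. What is collected, and when**

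- Baseline, both arms (METHODS; Appendix 5, service 1): structured questionnaire including items 35-38, plus Katz, IADL and MAL.
- Final assessment (Appendix 5, service 10): Katz, IADL and MAL only. METHODS also gives controls a final assessment, but no separate schedule for them exists.
- Events since baseline: no question in Katz, IADL, MAL or the questionnaire asks about a fall, injury, new stroke or hospital admission.
- Analysis of harm by arm: none in DATA ANALYSIS.

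Change in function can be computed in both arms. Change in pain or sensation, and event counts, cannot.

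**2. Planned contacts**

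- Intervention: services 1 and 10 (assessments) plus services 2 to 9 (remote) = 2 + 8 = 10.
- Control: initial and final assessment = 2.
- Between assessments: 8 v 0. After baseline, counting the final visit: 9 v 1.

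Interruption for health reasons concerns remote sessions, so it too can arise only in the intervention arm.

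**3. How unequal informal ascertainment could be (illustration)**

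Assumptions, none from the documents: the same true event rate in both arms; onset equally likely before each of the 9 post-baseline contacts of the intervention schedule; independent probability q that an event is mentioned at each contact after onset.

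- Intervention: (1/9) × Σ [1 − (1 − q)^m], m = 1 to 9. Control: q.
- q = 0.1: 0.387 v 0.1, ratio 3.9.
- q = 0.2: 0.615 v 0.2, ratio 3.1.
- q = 0.5: 0.889 v 0.5, ratio 1.8.
- q = 1: 1 v 1, ratio 1.

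The imbalance shrinks as the chance of mention at a contact rises. A fixed question put to everyone at the final assessment is meant to raise that chance equally in both arms.

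**4. What ten per arm can show if harm is asked about**

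The plan's 20 is a convenience sample with no stated alpha, power or effect size, so it cannot be re-derived beyond 20/2 = 10 per arm.

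- Upper bound for 0 events in 10, one-sided 95%: 1 − 0.05^(1/10) = 0.259. Upper limit of the two-sided 95% interval: 1 − 0.025^(1/10) = 0.308.
- Chance of seeing at least one event in an arm: 1 − 0.95^10 = 0.401 at a true rate of 5%; 1 − 0.90^10 = 0.651 at 10%.
- Two-sided Fisher test at 5%: the smallest significant split against 0/10 is 5/10 (p = 0.033). Exact power is 5.7% for 10% v 30% and 29.5% for 10% v 50% (assumed rates).

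Equal questioning therefore yields a fair description, not a test.

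**The case against.** The strongest reply is that this is a 20-person pilot of guidance sessions with no safety objective, that protective measures are in place, and that the questionnaire was meant to describe the sample, not to supply outcomes. With power of 5.7% in a plausible scenario, asking about harm would settle nothing. No harm table is planned either, so the plan as written produces no misleading comparison.

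Part of this stands. A reader might infer that referral is the only safety measure; it is not, since carer presence, interruption of sessions, the stability criterion and the safety session all count. They protect participants, but none of them records an event. A reader might also infer that patients bathe or dress during sessions; Appendix 5 describes guidance on technique, alongside mobilization. Nor will a pilot of this size recommend or reject telerehabilitation by itself. The false excess is a risk of informal reporting, not a planned result. Low power argues against a test, not against counting. The objective on challenges and limitations does not fill the gap, because it concerns delivery of telerehabilitation and so covers one arm.

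A further tempting inference is that travel to in-person assessments prevents a comparison of harm. The documents do not support it. Travel in both arms would be balanced. The control final visit has no stated mode, no section describes participants' journeys, and the travel clause is attached to remote guidance. It is a wording conflict to reconcile, no more.

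Two practical objections shape the remedy. Counting only at the final visit would miss participants who never reach it, and follow-up differs in length because some are assessed early. Also, item 35 has no severity grade, so repeating it cannot show worsening at the same site; a separate question on new or worse pain is needed.

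**Conclusion.** The point holds in this form: adverse events are not elicited, recorded or counted in either arm; pain and sensation are measured at baseline only; and contact between assessments is 8 v 0, so harm that surfaces informally would be ascertained unequally. The contact count follows directly from the schedule. The 1.8 to 3.9 ratio is illustrative and rests on the assumptions stated with it.

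A reader might conclude that the trial would hold no between-arm information on deterioration at all. That goes too far: loss of function is measured in both arms at both times on Katz, IADL and MAL. The gap is adverse events, pain and sensory change. It leaves the planned comparison of function untouched and is cheap to close, so it should be closed. Even then, ten per arm supports only counts with wide bounds.

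**What to change.** - At the existing final assessment in both arms, including participants assessed early because in-person care begins, repeat items 35-38 and ask one fixed, identical set of questions about the time since baseline: fall, injury, new or worse pain, new stroke, hospital admission.
- For participants who do not reach that visit, put the same questions to the participant or caregiver by telephone, in the same way in both arms. Where consent to contact has been withdrawn, report the number missing by arm.
- Report counts by randomised arm with each arm's follow-up time and an exact bound, as description and without a test. List events mentioned only in sessions separately.
- Separately, reconcile the RISK ANALYSIS statement on travel for appointments with the in-person assessments in METHODS and Appendix 5, and state the mode of the control arm's final assessment.

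Cost: an estimated five minutes within a visit scheduled for 60, one form page, a few telephone calls and a revised risk sentence. Two small downsides should be acknowledged: events are recalled over the follow-up period, and subjective answers are taken by an evaluator who, under METHODS, opens the allocation envelopes and so may know the arm.
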